The Neuroendocrine Tumor – Patient Reported Outcomes (NET-PRO) project is a prospective cohort study of all newly occurring GEP and lung NET cases aged 18 years and older diagnosed between 01/01/2019 and 12/31/2023. Participants will be recruited across 14 participating Patient Centered Outcomes Research Network (PCORnet) sites (from across 4 PCORnet clinical research networks), enrolling an average of 215 patients per site over the 3-year study period (~3,000 patients total), allowing up to a maximum of 60 months of follow-up. Participants will complete four online (or paper) surveys over 18 months; these surveys will focus on patient-reported outcomes, including questions on quality of life, treatment decisions, and experiences with cancer care. These survey data will be linked to individual participant level tumor and clinical characteristics from medical record data.

Project specific aims:

AIM 1: To describe the frequency of treatment regimens and examine their association with symptom burden and PROs and HRQoL outcomes. Enroll a cohort of patients to collect HRQoL and PROs data every 6 months, for 18 months (i.e.: baseline, 6, 12 and 18 month follow-up surveys). We will determine what combinations of therapy are being used, and the changes in symptoms, PROs and HRQoL associated with these different therapeutic choices.

AIM 2: To examine the association of patient, clinical, and tumor characteristics on treatment choice. We will use EMR data to investigate the impact of pre-existing comorbidities (i.e.: cardiovascular, renal and liver disease and diabetes), prognostic tumor factors (derived from cancer registry data) i.e.: stage, grade and nodal status, on the selection of therapies received and outcomes of survival and disease progression (collected via targeted chart reviews).

AIM 3: To compare the effectiveness of peptide receptor radionuclide therapy (PRRT) regimens on outcomes of renal toxicity, disease progression, and patient symptoms and HRQoL. We will utilize the combined PROs gathered in aim 1 and EMR data mined in aim 2 (i.e.: predictors), to compare the effectiveness of various PRRT treatment combinations and sequences, on outcomes of reduced creatinine clearance (renal toxicity), HRQoL and symptom burden, and survival and disease progression. We will further study the heterogeneity of these treatment effects by grade of differentiation (G1/2 vs G3) and NET subsite (GEP vs lung).

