4. STUDY DESIGN

4.1. Time anchors for study cohort

Study Period: 01/01/2019 to 12/31/2023 (5 years, max 60 months follow-up)

Index Date: Date of diagnosis of eligible NET tumor in the study period

Source Data Range: 01/01/2017-12/31/2023 (7 years, includes 2-year look-back period)

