4.2. Inclusion/Exclusion Criteria

To be eligible for this prospective cohort study subjects must meet **all** of the following criteria:

- i. Incident GEP-NET/Lung NET diagnosis*(see [Appendix A](#))
- ii. Diagnosed 01/01/2019-12/31/2023
- iii. No known prior GEP-NET/Lung NET diagnosis
- iv. Aged ≥ 18 years at diagnosis
- v. At least one site encounter within the study period of January 1, 2019 to December 31, 2023

* See [Appendix A](#) for a full list of International Classification of Diseases, Ninth Revision, Clinical Modification (ICD-9-CM), The International Classification of Diseases, Tenth Revision, Clinical Modification (ICD-10-CM) codes used to define a NET diagnosis. This appendix also lists the ICD-O-3 site codes and eligible histology codes for implementation in tumor registry data sources.

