- 3) **Progression-free survival (PFS).** Time to event data will be calculated from the index date (date of diagnosis) to the earliest of disease progression, death from any cause or end of study follow-up (12/31/2023). Acknowledging that patients may have more than one progression over the study period endpoints of median time to first progression (time from initiation of first-line therapy to progression) and time to second progression (time from second-line therapy initiation to progression) will be observed from targeted chart reviews at annual intervals. In collaboration with our clinician group we have discussed the various limitations of the application of the RECIST 1.1 criteria in NETs. These limitations include an overemphasis on tumor progression (given the low proliferation rate of GEP-NETs, monitoring changes in tumor size is suboptimal), and RECIST 1.1 criteria do not reflect overall tumor load or response to therapy in metastatic patients (i.e.: issues with clinical significance of radiologic progressions). Optimizing the management of NET patients therefore requires considering clinical, biological, and pathological aspects of the tumor. We have therefore chosen to categorize disease progression as DISEASE CONTROL (complete or partial response & stable disease), PROGRESSION (with no treatment change), PROGRESSION (with treatment change), and INDETERMINATE. This clinician-anchored approach has been found to be an optimal and valid method (versus RECIST1.1) for evaluating real-world tumor burden endpoints from EMR data [55].
[Time Frame: median time to progression, assessed annually via chart review]
- 4) **Overall Survival (OS).** Time to event data will be calculated from the date of diagnosis (index date) to the date of death from any cause, or end of study follow-up (12/31/2023). Death and vital status (death date, cause of death) will be pulled from the death table, and death cause table in the CDM. This data may be supplemented from site linkage to the social security death index or cancer registry sources (where possible). Given the prospective nature of the study we also have potential for passive surveillance/follow-up with participant/next of kin with information collected on our follow-up questionnaires.
[Time Frame: Up to 5 years]

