B4	Submit updated Recruitment Plan in PCORI Online.	Elements in the recruitment plan should, at a minimum, include the following: a. Timeline b. Total target sample size for primary analysis c. Name and # study sites d. Historical patient volume and estimated eligible N across study sites e. Estimated yield/consent f. Estimated lost to follow up/attrition g. Estimated monthly enrollment	8/31/2021	9/2/2021	
B5	Select and register project at appropriate site for the study design (Clinicaltrials.gov, RoPR, or other as approved by PCORI before study start date).	Submit Study Identification Number and the Primary Completion Date to PCORI. List PCORI as a collaborator so that PCORI's role as the funder (not sponsor) can be identified and tracked.	8/31/2021	9/30/2021	
B6	Submit IRB approval in PCORI Online (Continuing approval submitted annually).	Submit IRB approval of revised study protocol via the PCORI Online system.	9/1/2021	8/16/2021	
B7	Analytic plan	Submit revised analytic plan specifying aims, target population, outcomes	9/30/2021		4/30/2022
B8	Develop, finalize, and submit copy of study protocol in PCORI Online.	Refer to the PCORI Methodology Standards for required elements of the study protocol.	9/30/2021	4/13/2022	
B9	Obtain PCORnet study designation	Obtain and comply with designation requirements.	9/30/2021	6/2/2021	
B10	Refine research questions with rare disease community and other stakeholder input	Submit summary report describing input provided by rare disease community, patient, and other stakeholder partners into the selection and refinement of the research question, including the target population, interventions, and outcomes.	9/30/2021	12/21/2021	
B11	Begin recruitment.	Demonstrate the ability to obtain consent from the target population.	9/30/2021		4/29/2022
B12	Enroll first patient.		9/30/2021		4/29/2022

Milestone - Deliverable ID	Milestone - Deliverable Name	Description	Due Date	Completion date	Projected Completion Date
B13	Program and configure patient health record (PHR) portal for consent and baseline surveys	UICC staff will program consent functionality and baseline surveys in the PHR portal	9/30/2021		4/13/2022
B14	Execute Data Use Agreements (DUAs)	DUAs with institutions owning data are complete.	11/15/2021		5/31/2022

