- This phenotype was designed to maximize positive predictive value so it would be appropriate for recruitment via electronic or ground mail without prior confirmation of eligibility through chart review or clinic visit.
- The phenotype identifies patients with at least one ICD code in their electronic medical record (EMR)/billing records that specifies a GEP or lung NET. To mitigate the effect of incidental coding errors, at least two NET codes (which may or may not specify the site of the NET; see code descriptions in the Appendix) must be present, and the patient’s first and last NET code must be more than 30 days apart.
- The first NET code for a patient is presently required to be dated on or after 01JAN2019. This increases the likelihood that the patient’s NET diagnosis will be in the required 2019-2023 study window.
- This phenotype should be applied for all patients who are not known to have died.
- The lung NET High PPV phenotype had a PPV of 92% and the GEP NET High PPV phenotype had a PPV of 90-98% when compared with chart review at The University of Iowa. The estimated sensitivity was 59.0% and 45.2%, respectively (see Technical Details Box 1 for further information)

Technical Details Box 1. Performance of Phenotypes that use Diagnosis Codes in EHR Data (research warehouses or CDM)

1. High PPV Phenotype

Estimating the Positive Predictive Value of the High PPV Phenotype

The University of Iowa (UI) team conducted a chart review to validate a 15% random sample of cases identified with this phenotype over a five-year period. This was done separately for lung (N = 13) and GEP NETs (N = 51).

- Of the 13 cases identified by the phenotype as having lung NETs, 12 had diagnoses that were unequivocally confirmed on chart review (i.e., the chart described pathological confirmation of a lung NET). This corresponds to a PPV of 92%. The single case that was not confirmed had a pancreatic NET.
- Of the 51 cases identified by the phenotype as GEP NETs, 46 had diagnoses that were unequivocally confirmed on chart review. This corresponds to a PPV of 90%. There were two other cases that had pathological evidence of a NET with an unknown primary location. An additional two cases had a suspected NET with no pathological confirmation on the chart. If these four cases are considered “hits”, PPV increases to 98%. For the one remaining case, the chart contained contradictory and ambiguous information about the patient’s tumor.

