P tumor site	
TUMOR table or source data equivalent (NAACCR #400 - Primary Site)
 
Sites that use the PCORnet tumor table must establish a link to a table with the identifying data that is necessary for recruitment; the tumor table itself is deidentified.
 
Tumor registries generally do not store the decimal in the ICD-O-3 site codes, but this may vary between hospitals.
	
GEP tumor site PRIMARY_SITE_N400 in ('C160','C161','C162','C163','C164','C165','C166','C168','C169','C170','C171','C172','C173','C178','C179','C180','C181','C182','C183','C184','C185','C186','C187','C188','C189','C199','C209','C250','C251','C252','C253','C254','C257','C258','C259','C260','C268','C269');

Criterion	Logic/Notes	Defined
2. NET histology	
Basis: CDM TUMOR table or source data equivalent (NAACCR #522)
 
Some sites may store histology in the first four characters of the morphology variable (NAACCR #521 Morph--Type&Behav ICD-O-3). This variable is not included in Version 1.2 of the PCORnet tumor table.
	
HISTOLOGIC_TYPE_ICD_O3_N522 in ('8150','8151','8152','8153','8155','8156','8157','8240','8241','8242','8246','8249');

3. Diagnosed between 01/01/2019-12/31/2023	
Basis: CDM TUMOR table or source data equivalent
	
substr(DATE_OF_DIAGNOSIS_N390,1,4) in ('2019', '2020', '2021', '2022', '2023');

Criterion	Logic/Notes	Defined
	(NAACCR #390)	
4. Aged ≥ 18 years at diagnosis	Basis: CDM TUMOR table or source data equivalent (NAACCR #230)	input(AGE_AT_DIAGNOSIS_N230,3.) ≥ 18 ;

Other Recruitment Methods

Direct recruitment of eligible patients attending clinic (i.e., recently diagnosed), or at a routine follow-up appointment (i.e., prevalent cases) (see Protocol 4.3.1).

This approach will require a liaison with the practice clinics to assess patient appointments and coordinate with the clinical team to introduce the study in-person and supply a study packet/e-mail invitation. Provision of specific guidance on this is difficult, as the process will differ according to the logistics of each site. Further guidance on this route will be disseminated and discussed with study coordinators and the recruitment monitoring workgroup.

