APPENDIX C: Pre- and Post-Consent Contacts

Activity (Responsible Entity)	Contact	Mode(s)	Timing
Pre-Consent Contacts (Sites) Population: 
 • Did not consent, and • Did not decline, and • Is not deceased, and • Did not identify as ineligible, and • Did not indicate they need more time 	Invitation Contact #1	Email, EMR messaging, in-person (letter or study packet), mailed letter	N/A
	Invitation Contact #2	Email, EMR messaging, in-person (letter, study packet, or continued interest query), mailed letter, phone	7 days after Invitation Contact #1
	Invitation Contact #3		7 days after Invitation Contact #2
	Invitation Contact #4		7 days after Invitation Contact #3
	Invitation Contact #5		7 days after Invitation Contact #4
	Invitation Contact #6		7 days after Invitation Contact #5
Post-Consent Info (Sites) Population: 
 • Consented, and • Did not withdraw, and • Is not deceased, and • [Email not provided in Step 3, or phone or address info not provided in Step 4] 	N/A	Site to provide email, phone, address info in UICC REDCap for UICC to contact subject	7 days after Consent was signed
Post-Consent Reminder Contacts (UICC) Population: 
 • Consented, and • Did not withdraw, and • Is not deceased, and • Did not complete Survey #1 	Reminder #1	Email, mailed letter, phone	7 days after Consent was signed
	Reminder #2		7 days after Reminder #1
	Reminder #3		7 days after Reminder #2
	Reminder #4		7 days after Reminder #3
	Reminder #5		7 days after Reminder #4
	Reminder #6		7 days after Reminder #5
Survey #2/3/4 Contacts (UICC) Population: 
 • Consented, and • Did not withdraw, and • Is not deceased, and • Completed Survey #1 	Reminder #1	Email, mailed letter, [contact] months minus 3 days) after completion of Survey #1
	Reminder #2		7 days after Contact #1
	Reminder #3		7 days after Contact #2
	Reminder #4		7 days after Contact #3
	Reminder #5		7 days after Contact #4
	Reminder #6		7 days after Contact #5

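### Overall survival is counted from diagnosis in patients who must be alive to consent, with no delayed entry, so absolute survival is overstated

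*Protocol*

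**What the plan says.** Section 7.2, item 4, defines OS: "Time to event data will be calculated from the date of diagnosis (index date) to the date of death from any cause", or to the end of follow-up on 12/31/2023. Section 9.1.2 assigns it a Cox regression model and does not say when a patient enters the risk set.

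Several other places determine who can be in that analysis:

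- Section 4.2 admits patients "Diagnosed 01/01/2019-12/31/2023".
- In Table 8 (Section 11), milestone B12, "Enroll first patient", was due 9/30/2021 and is projected for 4/29/2022.
- Section 5.2 defines enrolment as completing consent and contact information. Under Sections 5.7.3 and 5.8 the patient signs.
- Appendix B says of the high-PPV algorithm: "This phenotype should be applied for all patients who are not known to have died". Appendix C lists "Is not deceased" among the conditions for a pre-consent contact.
- Appendix B also allows recruitment "at a routine follow-up appointment (i.e., prevalent cases"), alongside the recently diagnosed cases sought under Section 5.3.

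The synopsis describes the design as "allowing up to a maximum of 60 months of follow-up", and Section 4.1 gives the study period as "01/01/2019 to 12/31/2023 (5 years, max 60 months follow-up"). The only survivor-bias measure is in Section 9.3: time-dependent variables for treatment and confounders.

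**The concern.** This is left truncation handled as if it were complete follow-up from diagnosis. A patient diagnosed in 2019 who died in 2020 could never enter the cohort, while one diagnosed on the same day who lived to consent in 2022 enters with more than three years of survival already credited. The deaths are missing, but the survivors' person-time stays in the denominator.

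The time-dependent variables in Section 9.3 place treatment changes correctly in time. They do not remove the period before consent from the risk set.

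At stake is any absolute survival figure from diagnosis. Regimen comparisons would be affected if the lag from diagnosis to consent differs between regimens, which the documents neither show nor exclude.

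**Working it through.** **No plan figure to reproduce.** Table 4 lists power for OS as NA, and no death rate, expected survival or consent-lag distribution is given. The dates can be checked exactly; the size of the bias can only be illustrated.

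**Step 1: dates** (1 month = 30.4375 days)

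- First eligible diagnosis to projected first enrolment: 01/01/2019 to 4/29/2022 = 1,214 days = 39.9 months that must be death-free.
- Projected first enrolment to OS cut-off: 4/29/2022 to 12/31/2023 = 611 days = 20.1 months, the longest period in which any death can be observed.
- Using the 9/30/2021 due date instead gives 33.0 and 27.0 months. The problem remains.

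**Step 2: mechanism.** Let λ be a constant death rate and *p* the pre-consent share of person-time. Deaths occur only after consent, so the rate counted from diagnosis is λ(1 − *p*).

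Assumptions for this run: diagnoses uniform over 60 months, exponential survival with λ = −ln(S₅)/60, where S₅ is 5-year OS, and consent no earlier than 4/29/2022. Consent comes either within 3 months of first becoming possible (prompt) or is spread evenly to 12/31/2023 (spread).

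- Prompt: *p* ≈ 0.49, so the rate is about 0.51 of the truth.
- Spread: *p* ≈ 0.71 to 0.72, so it is 0.28 to 0.29 of the truth.

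True OS at 36 months is S₅^(36/60):

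| Assumed 5-year OS | True 36-month OS | As written, prompt / spread | Delayed entry at consent |
|---|---|---|---|
| 90% | 93.9% | 97.1% / 98.4% | 93.9% / 93.8% |
| 70% | 80.7% | 90.3% / 94.7% | 80.7% / 80.8% |
| 50% | 66.0% | 81.6% / 89.5% | 66.1% / 66.1% |

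**Step 3: a second illustration at 24 months.** Assumptions: exponential survival, enrolment uniform from 4/29/2022 to 12/31/2023, and 0%, 25% or 50% of enrollees diagnosed more than 12 months before consent. The truth is 0.5^(24/median).

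| Assumed median OS | True | As written (0 / 25 / 50%) | Overstatement, points |
|---|---|---|---|
| 60 months | 75.8% | 81.5 / 87.9 / 92.1% | 5.7 / 12.1 / 16.3 |
| 120 months | 87.1% | 90.3 / 93.7 / 95.9% | 3.2 / 6.6 / 8.8 |

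Delayed entry is within 0.3 points of the truth. The longer medians were chosen because Section 1.1.1 describes prolonged survival. Medians of 24 to 36 months would give 8–10, 18–23 and 24–31 points.

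**Step 4: hazard ratios.** With the same consent timing in both groups, a true ratio of 1.00 is estimated at 0.996 to 1.008, and a true 0.67 at 0.64 to 0.67.

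**Step 5: progression-free survival (PFS).** PFS from diagnosis is also biased upward, because patients who die before consent are lost. Chart review (Section 6.2) can, however, capture progressions that precede consent. In illness-death simulations with assumed rates, the PFS event rate was 0.88–0.95, 0.78–0.91 and 0.71–0.90 of the truth at 0, 25 and 50% prevalent, against 0.61–0.62, 0.44–0.45 and 0.35 for OS. The medians from start of a therapy line in Section 7.2, item 3, were not simulated.

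**Step 6: end of follow-up.** OS and PFS stop at 12/31/2023, but full enrolment (G1) is due 2/1/2024, 32 days later. Section 6.1 requests data in late 2023 yet wants about 36 months after joining. For the first projected enrollee that ends 4/29/2025, 303 days (10.0 months) after data collection must be complete on 6/30/2024 (G3).

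**The case against.** **The entry time could be left to a later SAP.** A left-truncated Cox model is compatible with the wording of Sections 7.2 and 9.1.2, and Section 9.3 says the plan will be refined. But Section 9 is itself headed as the statistical analysis plan, it fixes the model while Section 7.2 fixes the time origin, and Section 13.1 requires analyses to adhere to the plan. Applied as written, the rule is biased.

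**No survival curve, median or rate for OS is promised.** This is correct. The planned Cox comparison is little affected when consent timing is equal across groups. OS is secondary, and Section 9.2.2 calls Aim 2 exploratory. This limits the severity and stands.

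**The sizes are assumed and have no firm lower bound.** This also stands. With a consent lag uniform over 0 to 6 months, the 24-month overstatement falls to 2.8 points (78.6 against 75.8%) at median 60 months and 1.6 points (88.7 against 87.1%) at median 120. Short lags are plausible for new cases, since Section 5.3 has queries run every two to four weeks. The prevalent shares are assumptions, and no passage supports medians of 24 to 36 months.

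**Sixty months is literally possible when the index date is diagnosis.** True, but that is calendar time since diagnosis, not time in which a death can be observed. Taking 6/30/2024 as the end gives 26.1 observable months, still far short of 60.

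**Conclusion.** The concern holds. The time origin, the consent requirement and a Cox model without an entry time together credit survivors with time in which they could not have been seen to die. The date results (39.9 months, 20.1 months and the conflicting end dates) need only the protocol's own dates, the start being a projection.

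The bias in absolute OS is upward in every scenario run, provided consent timing is independent of later death risk given survival to consent. Its size cannot be determined from the protocol. Under the assumptions above it ranges from about 2 points, with quick consent and long survival, to 16 points at 24 months for median OS of 60 to 120 months. Hazard ratios are nearly unaffected under equal consent timing; under unequal timing they would be biased by an unknown amount. Because OS is secondary and Aim 2 exploratory, this is a should-fix.

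**What to change.** **OS (Sections 7.2 item 4 and 9.1.2).** Keep time since diagnosis as the scale and enter each patient into the risk set at the consent date, in the Cox model and in any Kaplan-Meier estimate. Report OS from consent as a sensitivity analysis. State the assumption that consent timing is independent of prognosis given covariates, and adjust for site, stage and grade.

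**PFS (Section 7.2 item 3).** Do not drop pre-consent progressions by default. Either state the survivor-selection limitation or use an illness-death analysis in which truncation acts on death. Delayed entry at consent discarded 33 to 71% of first PFS events in the simulations, so it belongs only in a sensitivity analysis.

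**Dates.** Reconcile the 12/31/2023 cut-off with enrolment to 2/1/2024, the data period of about 36 months after joining, and the 6/30/2024 close of data collection.

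**Cost.** For OS, a short paragraph: the e-signature date is already kept (Section 5.7.3), and paper consents are dated (Section 5.8). Intervals widen. With 3,010 patients and median OS of 60 months, the 95% half-width at 24 months rises from 1.2–2.2 to 3.4–4.2 points, while a bias of 6 to 16 points falls to 0.3 or less. It is not a complete cure. If patients within 6 months of death are half as likely to consent (assumed), delayed-entry OS at 24 months is still 3 to 7 points too high for medians of 60 to 120 months, against 5 to 18 without it. For PFS, the limitation costs a sentence, and a multistate analysis is more work.

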6.1. EMR data – Clinical and billing data from the PCORnet CDM

The PCORnet CDM is a key component of the PCORnet Distributed Research Network infrastructure, and will serve as the primary data source for the NET-PRO study. In late 2023, the UICC will request data from sites on all enrolled subjects. Data will include demographics, toxicity outcomes, vitals and vital status, treatments, laboratory tests and results, health conditions (comorbidities), tumor characteristics (from tumor registry variables/tumor tables in the CDM), disease status, and encrypted IDs used to link patient care across sites. The data will cover the period two years prior to the subject's NET diagnosis through approximately 36 months after the date they joined the study. Note, as per the inclusion criteria, we will not be excluding patients who do not have 2 years of look-back data prior to their diagnosis date. Table 2 summarizes the variables that will be obtained from the CDM. The specific code lists for derivation of these variables in the CDM will be later specified and distributed to sites.

Table 2: Patient, clinical and tumor variables that will be measured from the CDM

Concept/variable		CDM Tables
Demographics	Date of birth, sex, Hispanic, Race	Demographic Table
Toxicity outcomes	Acute renal failure, dialysis, liver failure	Diagnosis Table
Vitals	Height, weight, systolic and diastolic blood pressure, smoking	Vitals Table
Cancer Treatments	Somatostatin Analogues (SSAs) (octreotide, lanreotide, pasireotide) Bevacizumab, Cytotoxic chemotherapy, Everolimus, Interferon alpha, Hepatic Artery Bland-, Chemo- or radioembolization, PRRT -Lutetium Lu-177 dotatate, PRRT-Yttrium-90 Dotatoc, Small molecule TKIs, Telotristat ethyl)	Dispensing, prescribing, procedures, and medications administered Tables
Lab values	Alanine transaminase (ALT), Albumin and Microalbumin Albumin/Creatinine and Microalbumin/creatinine Ratio, Alkaline phosphatase (ALP), Aspartate transaminase (AST), AST/ALT ratio, Blood Urea Nitrogen, Chromogranin A, Cystatin C, Hemoglobin, Ki-67, Lymphocytes, Pancreastatin, Serum or Blood Creatinine, Somatostatin, Total Bilirubin	Lab results

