- 2) **European Organization for Research and Treatment of Cancer - Quality of Life Questionnaire - Neuroendocrine Carcinoid Module (EORTC QLQ-GI.NET21)** The EORTC QLQ-C30 can be used in conjunction with the EORTC QLQ-GI.NET21 specific questionnaire, which comprises a total of 21 items: four single-item assessments relating to muscle and/or bone pain (MBP), body image (BI), information (INF) and sexual functioning (SX), together with 17 items organized into five proposed scales: endocrine symptoms (ED; three items), GI symptoms (GI; five items), treatment-related symptoms (TR; three items), social functioning (SF21; three items) and disease-related worries (DRW; three items). Responses to the QLQ-GINET21 will be linearly transformed to a 0-100 scale using EORTC guidelines, with higher scores reflecting more severe symptoms.

[Time Frame: Change in mean score across baseline, 6, 12, and 18 month time points.]

- 3) **Sequencing of treatment regimens from electronic medical records.** This will involve identifying which treatments a patient used during their follow-up, and also in what order they received treatment. Dates and types of therapy initiated will be pulled from each patients EMR in reference to the patient’s index date (date of diagnosis). We will also be asking patients about their treatments (self-reported) in the baseline survey to ascertain potential missed therapies in the EMR. We will be comparing the frequency (N) and proportion (%) of use of a variety of therapies (i.e.: SSAs, bevacizumab, cytotoxic chemotherapy, everolimus, Interferon alpha, embolization, PRRT, small molecule TKIs) and the effects of their ordering/sequencing on outcomes of symptom burden and HRQoL.

[Time Frame: Up to 5 years, baseline to end of follow-up]

- 4) **Renal function.** Glomerular filtration rate (GFR) is the best overall index of kidney function. Normal GFR declines with age, and varies according to sex, race and body size. We will calculate creatinine clearance loss [54] by combining individual level CDM and enrollment questionnaire data on sex, race, height, weight and serum creatinine mg/dl laboratory values at regular intervals before and after PRRT cycles until the end of follow-up.

[Time Frame: Change in eGFR from baseline to end of follow-up.]

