- 5) **Adverse toxicities.** We will assess incident acute renal failure, dialysis and liver failure during study follow-up (from diagnosis codes in the CDM). The occurrence of these events will be compared in reference to the treatment regimens received.
[Time Frame: Up to 5 years]

Table 4: Overview of Primary and Secondary outcomes for NET-PRO by project aims

Primary or Secondary	Name of Outcome	Specific Measure(s)/ Instrument(s) to Be Used	Timepoints (mths)	PROMIS and/or Core Outcome Set ?	Powered Yes/No/NA
Aim 1					
Primary	Health related Quality of Life (HRQoL)	EORTC QLQ-C30 EORTC QLQ-GI.NET21	0, 6, 12, 18	Yes	Yes
Secondary	Symptom inventory	Norfolk Carcinoid Symptom Score [49] Norfolk Carcinoid Symptom Score [49]	0, 6, 12, 18	No	No
Secondary	Experiences of care	Physician communication, coordination and responsiveness of care [62]	0, 6, 12, 18	No	No
Aim 2					
Primary	Sequencing of treatment regimens	-	0-60	No	Yes
Secondary	Progression-free survival	Time to event (Categorization of stable disease, disease progression with no change in treatment, disease progression with changes in treatment, and indeterminate)	0-60	No	Yes
Secondary	Overall survival	Time to event	0-60	No	NA
Secondary	Adverse toxicities	Incident acute renal failure, dialysis and liver failure during follow-up	0-60	No	NA
Aim 3					
Primary	Renal function	Creatinine clearance loss (per/Yr)	0, 6, 12, 18	No	Yes
Secondary	Adverse toxicities	CDM diagnosis codes for acute renal failure, dialysis and liver failure during follow-up	Up to 60	No	No
Secondary	Health related Quality of Life (HRQoL)	Changes in HRQoL and symptom scores	0, 6, 12, 18	No	No
Secondary	Renal toxicity (creatinine clearance) by PRRT isotope	Creatinine clearance loss (per/Yr) 177Lu vs 90Y	Up to 60	No	No
Secondary	Renal toxicity of PRRT by primary tumor location & grade 3 disease	Creatinine clearance loss (per/Yr) GEP-NETs vs lung NETs and G3	Up to 60	No	No

NA: Not applicable

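### The secondary adverse-toxicity outcome takes dialysis and organ failure from diagnosis codes alone, although procedure records are already drawn on and liver laboratory results go unused

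*Protocol*

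**What the plan says.** Section 7.2 item 5 defines the secondary outcome of adverse toxicities: "We will assess incident acute renal failure, dialysis and liver failure during study follow-up (from diagnosis codes in the CDM"). It then states the use: "The occurrence of these events will be compared in reference to the treatment regimens received". In Table 4 the outcome appears twice. The Aim 2 row names no source; the Aim 3 row specifies "CDM diagnosis codes for acute renal failure, dialysis and liver failure during follow-up". In Table 2 (section 6.1) the toxicity row, "Acute renal failure, dialysis, liver failure", is assigned to the Diagnosis Table and to nothing else.

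Other rows of Table 2 show what else is extracted for the same patients. Cancer treatments come from "Dispensing, prescribing, procedures, and medications administered Tables". The laboratory row includes "Serum or Blood Creatinine, Somatostatin, Total Bilirubin", along with ALT, AST, ALP, BUN and cystatin C.

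Renal function is also a separate, laboratory-based outcome. Section 7.1 item 4 builds creatinine clearance loss from "serum creatinine mg/dl laboratory values at regular intervals before and after PRRT cycles until the end of follow-up". Table 4 adds two secondary creatinine-clearance outcomes for Aim 3, one by isotope ("Creatinine clearance loss (per/Yr) 177Lu vs 90Y") and one by primary tumor location and grade 3 disease. There is no laboratory-based liver outcome.

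**The concern.** The source of these three events is fixed in the protocol itself, in three places, and it is narrower than it needs to be. Dialysis is something done to a patient, so its natural record is a procedure record. A course of dialysis that was billed as a procedure but never given a matching diagnosis code would not be counted. For the liver, coded failure is the only planned measure, although section 1.1.3 names hepatotoxicity among the treatment harms and section 8 lists embolization among the regimens compared.

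Two things are at stake. Missed events lower the reported absolute risk and cost precision. If capture also differs by regimen, for example because some patients are followed more closely than others, the comparison of regimens mixes toxicity with recording.

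**Working it through.** **Text check.** The sources named for each outcome, side by side:

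| Outcome | Place in protocol | Source named |
|---|---|---|
| Acute renal failure, dialysis, liver failure | 7.2 item 5; Table 2; Table 4 (Aim 3) | Diagnosis codes only |
| Cancer treatments | Table 2 | Procedures and three medication-related tables |
| Renal function (Aim 3 primary) | 7.1 item 4 | Serum creatinine results |
| Renal toxicity by isotope; by tumor location and grade 3 (Aim 3 secondary) | Table 4 | Creatinine clearance |
| Liver function | None | ALT, AST and bilirubin extracted, not used in an outcome |

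The single-source definition is therefore confirmed for the adverse-toxicity outcome and for nothing wider.

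**Size.** The protocol states no event rate, code sensitivity or power for this outcome (Table 4: not applicable for Aim 2, not powered for Aim 3), so there is no figure to reproduce. What follows illustrates the mechanism under assumptions.

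Inputs from section 9.2: about 300 PRRT patients out of 3,010, leaving 3,010 − 300 = 2,710 others. Assumed: the true risks, the capture probabilities (sensitivities, Se), and no false-positive codes.

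Observed risk = true risk × Se. Observed risk ratio = true risk ratio × Se₁/Se₀.

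*Equal capture.* Se₁/Se₀ = 1, so the risk ratio is unbiased and only events are lost. At a true risk of 5% in 300 patients there are 15 true events. Observed: 15 × 0.9 = 13.5, 15 × 0.7 = 10.5, 15 × 0.5 = 7.5. Power for a true 10% against 5% (300 against 2,710, two-sided 5%) falls from 0.90 with full capture to 0.87, 0.79 and 0.66.

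*Unequal capture, no true difference.* The spurious ratio is Se₁/Se₀:

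| Se₁ vs Se₀ | Spurious risk ratio | Chance of a false significant result at 5% true risk |
|---|---|---|
| 0.9 vs 0.7 | 1.29 | 0.16 |
| 0.7 vs 0.5 | 1.40 | 0.21 |
| 0.9 vs 0.5 | 1.80 | 0.52 |

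The last column and the power figures use Φ[(d − 1.96·se₀)/se₁], where d is the difference in observed risks, se₀ its standard error with pooled variance and se₁ that with unpooled variance. For the middle row:

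- Observed risks: 0.05 × 0.7 = 0.035 and 0.05 × 0.5 = 0.025, so d = 0.010.
- Pooled risk: (10.5 + 67.75)/3,010 = 0.0260, giving se₀ = 0.00968; se₁ = 0.01103.
- (0.010 − 1.96 × 0.00968)/0.01103 = −0.81, and Φ(−0.81) = 0.21.

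For the middle row, the chance is 0.13 at a true risk of 2% and 0.34 at 10%.

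**Which comparisons are exposed.** In Aim 3 (section 8.3, and section 9.1.3 for isotope) the contrasts are between PRRT regimens, so both sides receive PRRT, and closer renal follow-up of PRRT patients would not by itself separate them. The adverse-toxicity outcome also belongs to Aim 2, where regimens across all therapy classes are compared. Unequal capture matters mainly there. The creatinine-clearance outcome is tied to PRRT cycles and does not cover the other regimens.

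**The case against.** A reader might infer that renal toxicity in this study rests on diagnosis codes only. It does not: the Aim 3 primary outcome and two secondary outcomes use laboratory creatinine clearance, and section 6.2 allows chart abstraction of creatinine, BUN and eGFR around PRRT cycles. That part of the objection stands in full and limits the point to the adverse-toxicity outcome.

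A reader might also infer that events are shown to be under-counted, or that the PRRT comparison is shown to be biased. Neither is supported. No sensitivity is given for these codes, diagnosis codes for dialysis status may catch some cases, and false-positive codes could push the reported risk upward. The only in-document evidence on capture is that ICD codes alone found 65% of lung NET cases in one registry (section 10.1), which concerns tumor diagnosis and not toxicity.

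The code lists are to be specified later (section 6.1), and detailed event algorithms often sit in an analysis plan. This answers only part of the point, because the list is deferred while the table from which it will be drawn is already named.

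Finally, it is tempting to make laboratory grades the main definition. The objection to that stands. It would change the outcome from clinical failure to laboratory abnormality, and creatinine sampling is itself planned around PRRT cycles, so a laboratory-defined event could depend on monitoring more than a coded one does.

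**Conclusion.** The point holds for the secondary adverse-toxicity outcome. Dialysis is sought in one table when a second, more natural one is already in use, and liver toxicity has no laboratory support although the results are extracted. Size and direction of bias cannot be derived from the protocol. The spurious ratio of 1.4 rests on assumed capture of 70% against 50% with no false positives; if capture is equal, the ratio is unbiased and the cost is lost events and power. The importance is moderate: the outcome is secondary and not powered, but it is compared between regimens in a study whose stated purpose includes reducing toxicity.

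**What to change.** Amend Table 2, section 7.2 item 5 and Table 4 as follows.

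1. Identify dialysis from the Procedures and Diagnosis tables together.
2. Keep the coded definitions of acute renal failure and liver failure as the main definitions.
3. Add a supporting sensitivity analysis of renal and liver events from the creatinine, bilirubin and ALT/AST results already extracted. Fix the criteria with the Clinician Group before outcome data are seen.
4. Report laboratory testing frequency by regimen beside that analysis.

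The cost is one procedure-code list and one derivation script on data already in the planned extract. The downside is that the laboratory version also depends on how often each regimen's patients are tested, which is why it should stay supportive and why testing frequency must be shown with it.
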